6.1 Software

SAS for Windows Release 9.3 (Cary, NC) will be used for all analyses.

6.2 Calculating scores and z-scores

If a large percentage of data is missing for any item, we will exclude that item from the total score. For all other missing item scores, we will impute the scores based on the other items in the same subscale. We will use the imputation method described in Raghunathan et al. (2001).

Z-scores of developmental variables will be calculated based on the distribution of the iLiNS-DOSE sample, by standardizing the distribution to a mean of 0 and standard deviation of 1.

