- 4. Hypotheses 1-3 will also be examined with regard to the prevalence of severe and moderate to severe delay in motor development, language development, socio-emotional development, and executive function.

3. Definition of the 18-month developmental outcomes

The gross motor score is calculated as the sum of 35 Kilifi Developmental Inventory (KDI) gross motor items, each scored 0 or 1 (sum of *Form 25a Q 5.1-5.2* and *5.6-7.12*). Severe delay is defined as the bottom 10% of our sample. Moderate to severe delay is defined as the bottom 25% of our sample.

The fine motor score is calculated as the sum of 34 KDI fine motor items, each scored 0 or 1 following Abubakar et al. (2008). Severe delay is defined as the bottom 10% of our sample. Moderate to severe delay is defined as the bottom 25% of our sample.

The psychomotor score is calculated as the sum of 69 KDI fine and gross motor items, each scored 0 or 1. Severe delay is defined in two ways: (1) the bottom 10% of our sample and (2) <-3 SD below the mean according to published norms from Kenya (Abubakar et al. 2008). Moderate to severe delay is defined in two ways: (1) the bottom 25% of our sample and (2) <-2 SD below the mean according to published norms from Kenya (Abubakar et al. 2008).

Language development is quantified as

- a. Vocabulary score, calculated as the sum of *Form 25c LANGVOCAB1* through *LANGVOCAB100*. Severe delay is defined as the bottom 10% of our sample.
 Moderate to severe delay is defined as the bottom 25% of our sample.
- b. Expressive vocabulary > 10 words vs. <= 10 words, derived from the vocabulary score
- c. Word combining (Has the child started combining words into sentences? 0 = not yet, 1 = sometimes, 2 = often) *Form* 25*c* Q 4.1

Socio-emotional development is calculated as the sum of *Form 25b PSED1* through *PSED19*. Severe delay is defined as the top 10% of our sample (a lower score indicates more advanced socio-emotional development). Moderate to severe delay is defined as the top 25% of our sample.

Executive function is calculated as

- a. A not B task total number correct, *Form 25a Q16.2*. Severe delay is defined as the bottom 10% of our sample. Moderate to severe delay is defined as the bottom 25% of our sample.
- b. A not B task total errors after set 1, Form 25a Q16.3
- c. A not B task total trials completed, *Form 25a Q 16.1*. If this variable is not normally distributed, another statistical approach will be used, such as creating a dichotomous variable

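### If any motor item is excluded for missing data, psychomotor delay judged by the Kenyan norms would be overstated or unchanged, never understated

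*SAP*

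**What the plan says.** Appendix 02, section 3 (Definition of the 18-month developmental outcomes) states: "The psychomotor score is calculated as the sum of 69 KDI fine and gross motor items, each scored 0 or 1". The components agree with this: 35 gross motor items, and for the other part "The fine motor score is calculated as the sum of 34 KDI fine motor items, each scored 0 or 1".

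Section 3 then defines psychomotor delay in two ways. One takes the bottom 10% (severe) or bottom 25% (moderate to severe) of the trial sample. The other is external: severe delay is "<-3 SD below the mean according to published norms from Kenya" and moderate to severe delay is "<-2 SD below the mean according to published norms from Kenya".

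Section 6.2 (Calculating scores and z-scores) has two rules for missing items. The first is "If a large percentage of data is missing for any item, we will exclude that item from the total score". The second is "For all other missing item scores, we will impute the scores based on the other items in the same subscale". It attaches no number to the first rule, does not exempt the norm-based definition, and does not mention rescaling the total or the norm. For standardised scores it says "Z-scores of developmental variables will be calculated based on the distribution of the iLiNS-DOSE sample".

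The shell of Table 3 in Appendix 02 has one psychomotor row per severity and does not say which definition of delay it reports.

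**The concern.** The external cut-off is a fixed number of points on the scale of the score to which section 3 applies it, the 69-item sum. Excluding an item shortens the trial's score but not the norm's. The second missing-data rule does not repair this, because it imputes only the items that are kept.

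The figure at risk is the one with absolute meaning. Every other delay outcome in section 3 has its overall prevalence fixed by construction at about 10% or 25%, so the norm-based psychomotor figure is the only delay prevalence that a reader could compare with another population. It also falls under hypothesis 4 of the appendix and the relative risks of section 5.4.

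**Working it through.** **Scale.** 35 + 34 = 69, which reproduces the stated length of the psychomotor score.

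**Direction.** Let T be the 69-item total and S the total after dropping k items. Each item is 0 or 1, so S = T minus the number of dropped items passed, and S ≤ T for every child. With the cut-off fixed at norm mean - c × SD (c = 2 or 3), every child below it on T is also below it on S. The share classed as delayed cannot fall. This needs no distributional assumption.

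**Size.** The documents give neither the norm mean and SD, nor item pass rates, nor the number of dropped items. The assumptions are a sample that otherwise matches the norm, normal scores, and dropped items with pass rate p. The mean total then falls by k × p points, and

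share below the cut-off = Φ(-c + k × p / SD).

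With no item dropped, the shares are Φ(-2) = 2.28% and Φ(-3) = 0.13%. Example for k = 3, p = 0.9, SD = 6: the shift is 3 × 0.9 / 6 = 0.45 SD, Φ(-1.55) = 6.06%, and 6.06 / 2.28 = 2.7.

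| Items dropped | Pass rate | Norm SD | Shift (SD) | Below -2 SD | Factor | Below -3 SD | Factor |
|---|---|---|---|---|---|---|---|
| 1 | 0.5 | 8 | 0.06 | 2.63% | 1.2 | 0.17% | 1.2 |
| 1 | 0.9 | 4 | 0.23 | 3.79% | 1.7 | 0.28% | 2.0 |
| 3 | 0 | any | 0 | 2.28% | 1.0 | 0.13% | 1.0 |
| 3 | 0.5 | 8 | 0.19 | 3.50% | 1.5 | 0.25% | 1.8 |
| 3 | 0.9 | 6 | 0.45 | 6.06% | 2.7 | 0.54% | 4.0 |
| 3 | 0.9 | 4 | 0.68 | 9.26% | 4.1 | 1.00% | 7.4 |

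The formula lowers every child's score by the same amount, so p is best read as the pass rate among children near the cut-off.

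**Item-level check.** A simulation of 69 binary items with assumed difficulties gave a full-score SD of about 7.1 and 2.5% below -2 SD. The table shows the share below -2 SD after dropping items.

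| Dropped | Fixed full-score cut-off | Cut-off re-derived on retained items | Total prorated to 69 |
|---|---|---|---|
| 1 easy | 3.3% | 2.4% | 2.4% |
| 3 easy | 5.9% | 2.2% | 4.3% |
| 5 easy | 9.7% | 2.0% | 5.6% |
| 3 middling | 2.7% | 2.7% | 1.9% |
| 5 middling | 3.0% | 2.1% | 1.5% |
| 3 hard | 2.5% | 2.5% | 1.8% |

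Three easy items multiply the share by about 2.4 (5.9 / 2.5). Middling items, passed by half of all children but by fewer near the cut-off, change it little. Hard items do not change it. Re-deriving the cut-off keeps the share at 2.0% to 2.7%. Proration under-corrects when three or five easy items are dropped and over-corrects for middling or hard ones.

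**Group comparison.** Assume a true benefit of 0.2 SD, 322 children per arm (1932 / 6) and the 0.45 SD shift above. At -2 SD the relative risk moves from Φ(-2.2)/Φ(-2) = 0.61 to Φ(-1.75)/Φ(-1.55) = 0.66. Expected control-arm events rise from about 7 (322 × 0.0228) to about 20 (322 × 0.0606).

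**The case against.** The strongest reply is that this is a contingency. The exclusion rule is conditional, nothing in the SAP says that any motor item met it, and all other missing items are imputed, which keeps the total at full length. A reader might infer that the plan does overstate psychomotor delay. The documents do not support that; they support only that it would be overstated, or unchanged, if an item were excluded.

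Second, the norm's scale is not shown. That it refers to the full 69-item sum is inferred from section 3 applying it to that sum. The inference is reasonable, but it is an inference. One could add that the SAP is merely silent on adjusting the norm. That does not remove the point: the two rules as written, followed literally, give the wrong classification.

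Third, a reader might infer that the arm comparisons are biased, or that individual children are called delayed because their own item was not recorded. Neither follows. An excluded item is removed for every child in every arm, so the effect is close to that of a less extreme cut-off and the contrast stays randomised. In the example above the attenuation is slight and the comparison gains events. This objection stands, and it limits the point to absolute prevalence.

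Fourth, the factors at -3 SD multiply a very small base: 0.13% of 1932 is about 2.6 children across six arms if the sample matches the norm. They should carry little weight. The point also touches one of two definitions of delay, for one score, among secondary outcomes.

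**Conclusion.** The plan is wrong as written, conditional on the exclusion rule being triggered. The direction is certain given 0/1 scoring and a norm on the 69-item scale. The size cannot be computed from the documents. It runs from nil, for items that few children near the cut-off pass, to roughly 1.5 to 4 times at -2 SD for three items with pass rates of 0.5 to 0.9 and a norm SD of 4 to 8, assuming normal scores and a sample that otherwise matches the norm.

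The damage is to the absolute, norm-based prevalence of psychomotor delay. The bottom 10% and 25% cut-offs and the within-sample z-scores adjust to whatever total results. Relative risks are attenuated at most modestly.

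**What to change.** Add to Appendix 02, section 6.2: exclusion of an item for missing data applies to the within-sample scores, z-scores and percentile cut-offs. Delay by the Kenyan norms is reported only when the psychomotor score is on the full 69-item scale, or when the norm mean and SD have been re-derived for the retained items. Otherwise the norm-based delay is not reported.

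Do not prorate a shortened total to 69 items, for the reason shown in the simulation. Imputing a heavily missing item to restore the full length is not an easy way out either, since section 6.2 declines to impute exactly those items.

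The cost is a sentence or two and a few lines of code. The downside is small: if an item is excluded and re-derived norms cannot be obtained, the norm-based figure may not be reportable.

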6.3 Multiple comparisons

The Tukey-Kramer adjustment method is used.

6.4 Confidence intervals

The same as that for the primary outcome analyses.

6.5 Interaction and effect modification

We will examine the same factors as that for the primary outcome analyses. In addition, we will examine the following effect modifiers:

- 1. Child stunting at enrollment (LAZ < -2)
- 2. Child wasting at enrollment (WHZ <-2)
- 3. Child 6 month iron deficient anemic, iron deficient non-anemic, non-iron deficient anemic, non-iron deficient non-anemic
- 4. Maternal education (we will examine the data to establish a cut-off)
- 5. Family care indicators (we will examine the data to establish a cut-off)

6.6 Covariate adjustment

The same procedure will be followed as for the main analyses, with three models rather than four models:

1. No covariate adjustment

- 2. Adjustment for child age at developmental assessment
- 3. Adjustment for child age at developmental assessment, baseline LAZ-score, and baseline WHZ-score and for any of the variables presented in tables 1a and 1b of the primary outcome Statistical Analysis Plan (SAP) showing statistically significant association (at p<0.1 level) with the developmental score

In addition to the variables in tables 1a and 1b of the primary outcome SAP, we will consider the following variables for inclusion:

- 1. Family care indicators score, if this score is not different between supplement groups.
- 2. For the KDI scores, the child's mood, interaction with the tester, and activity level during testing, if they are not different between supplement groups (*Form 25a Q 3.1 3.3*).
- 3. For the language scores, the child's primary language (Chichewa, Chiyao, English, or other) and the number of languages to which the child had been exposed (*Form 25c Q* 1.7-1.8).

7. References

- Kleinman, L. C., & Norton, E. C. (2009). What's the Risk? A simple approach for estimating adjusted risk measures from nonlinear models including logistic regression. *Health services research*, *44*(1), 288-302.
- Raghunathan, T. E., Lepkowski, J. M., Van Hoewyk, J., & Solenberger, P. (2001). A multivariate technique for multiply imputing missing values using a sequence of regression models. Survey Methodology, 27(1), 85-95.

8. Tables

Table 1 I	Results of the	ANCOVA com	paring developmenta	al scores in the intervent	ion groups at age 18 months.
10010 1 1	Leoseries or ente				Tom groups at age to monthly

Variable	Control	10g milk	20g milk	20g milk-	40g milk	40g milk-	P-value
		LNS	LNS	free LNS	LNS	free LNS	
Mean gross motor raw score (SD) ^y	xx.x ^x (xx.x)	xx.x ^x (xx.x)	$xx.x^{x}(xx.x)$	$xx.x^{x}(xx.x)$	$xx.x^{x}(xx.x)$	$XX.X^{X}(XX.X)$	X.XX
Mean gross motor z-score (SD) ^y	$xx.x^{x}(xx.x)$	$xx.x^{x}(xx.x)$	$xx.x^{x}(xx.x)$	$xx.x^{x}(xx.x)$	$xx.x^{x}(xx.x)$	$XX.X^{X}(XX.X)$	
Mean fine motor raw score (SD) ^y	$XX.X^{X}(XX.X)$	$xx.x^{x}(xx.x)$	$xx.x^{x}(xx.x)$	$xx.x^{x}(xx.x)$	$XX.X^{X}(XX.X)$	$XX.X^{X}(XX.X)$	X.XX
Mean fine motor z-score (SD) ^y	$xx.x^{x}(xx.x)$	$xx.x^{x}(xx.x)$	$xx.x^{x}(xx.x)$	$xx.x^{x}(xx.x)$	$xx.x^{x}(xx.x)$	$XX.X^{X}(XX.X)$	
Mean psychomotor raw score (SD) ^y	$xx.x^{x}(xx.x)$	$xx.x^{x}(xx.x)$	$xx.x^{x}(xx.x)$	$xx.x^{x}(xx.x)$	$xx.x^{x}(xx.x)$	$XX.X^{X}(XX.X)$	X.XX
Mean psychomotor z-score (SD) ^y	$xx.x^{x}(xx.x)$	$xx.x^{x}(xx.x)$	$xx.x^{x}(xx.x)$	$xx.x^{x}(xx.x)$	$xx.x^{x}(xx.x)$	$XX.X^{X}(XX.X)$	
Mean vocabulary raw score (SD) ^y	$xx.x^{x}(xx.x)$	$XX.X^{X}(XX.X)$	$xx.x^{x}(xx.x)$	$xx.x^{x}(xx.x)$	$xx.x^{x}(xx.x)$	$XX.X^{X}(XX.X)$	X.XX
Mean vocabulary z-score (SD) ^y	$xx.x^{x}(xx.x)$	$xx.x^{x}(xx.x)$	$xx.x^{x}(xx.x)$	$xx.x^{x}(xx.x)$	$xx.x^{x}(xx.x)$	$XX.X^{X}(XX.X)$	
Mean socio-emotional raw score (SD) ^y	$xx.x^{x}(xx.x)$	$XX.X^{X}(XX.X)$	$xx.x^{x}(xx.x)$	$xx.x^{x}(xx.x)$	$xx.x^{x}(xx.x)$	$XX.X^{X}(XX.X)$	X.XX
Mean socio-emotional z-score (SD) ^y	$xx.x^{x}(xx.x)$	$XX.X^{X}(XX.X)$	$xx.x^{x}(xx.x)$	$xx.x^{x}(xx.x)$	$xx.x^{x}(xx.x)$	$XX.X^{X}(XX.X)$	-
Mean A not B task total correct (SD) ^y	$xx.x^{x}(xx.x)$	$xx.x^{x}(xx.x)$	$xx.x^{x}(xx.x)$	$xx.x^{x}(xx.x)$	$xx.x^{x}(xx.x)$	$XX.X^{X}(XX.X)$	X.XX
Mean A not B task total correct z-score (SD) ^y	$XX.X^{X}(XX.X)$	XX.X ^x (XX.X)					

Mean A not B task errors (SD) ^y	$xx.x^{x}(xx.x)$	$xx.x^{x}(xx.x)$	$xx.x^{x}(xx.x)$	$xx.x^{x}(xx.x)$	$xx.x^{x}(xx.x)$	$xx.x^{x}(xx.x)$	X.XX
Mean A not B task errors z-score (SD) ^y	$xx.x^{x}(xx.x)$	$xx.x^{x}(xx.x)$	$xx.x^{x}(xx.x)$	$xx.x^{x}(xx.x)$	$xx.x^{x}(xx.x)$	$XX.X^{X}(XX.X)$	
Mean A not B task total trials completed (SD) ^y	$xx.x^{x}(xx.x)$	$XX.X^{X}(XX.X)$	$xx.x^{x}(xx.x)$	$xx.x^{x}(xx.x)$	$XX.X^{X}(XX.X)$	$xx.x^{x}(xx.x)$	X.XX
Mean A not B task total trials completed z-score (SD) ^y	$xx.x^{x}(xx.x)$	$XX.X^{X}(XX.X)$	xx.x ^x (xx.x)	$xx.x^{x}(xx.x)$	$XX.X^{X}(XX.X)$	$xx.x^{x}(xx.x)$	
Mean interaction with caregivers raw score (SD) ^y	$xx.x^{x}(xx.x)$	$XX.X^{X}(XX.X)$	$xx.x^{x}(xx.x)$	$xx.x^{x}(xx.x)$	$XX.X^{X}(XX.X)$	$xx.x^{x}(xx.x)$	X.XX
Mean interaction with caregivers z-score (SD) ^y	$xx.x^{x}(xx.x)$	xx.x ^x (xx.x)	xx.x ^x (xx.x)	xx.x ^x (xx.x)	xx.x ^x (xx.x)	$xx.x^{x}(xx.x)$	

^yFootnotes will report the covariates included for each outcome.

Variable	Coefficient	90 % CI	P-value
Difference in mean gross motor z-score in milk-free LNS compared to milk-containing LNS	XX.XX	xx.xx to xx.xx	X.XX
Difference in mean fine motor z-score in milk-free LNS compared to milk-containing LNS	XX.XX	xx.xx to xx.xx	X.XX
Difference in mean psychomotor z-score in milk-free LNS compared to milk-containing LNS	XX.XX	xx.xx to xx.xx	X.XX
Difference in mean vocabulary z-score in milk-free LNS compared to milk-containing LNS	XX.XX	xx.xx to xx.xx	X.XX
Difference in mean socio-emotional z-score in milk-free LNS compared to milk-containing LNS	XX.XX	xx.xx to xx.xx	X.XX
Difference in mean A not B task total correct z-score in milk-free LNS compared to milk-containing LNS	XX.XX	xx.xx to xx.xx	X.XX
Difference in mean A not B task errors z-score in milk- free LNS compared to milk-containing LNS	XX.XX	xx.xx to xx.xx	X.XX
Difference in mean A not B task total trials z-score in milk-free LNS compared to milk-containing LNS	XX.XX	xx.xx to xx.xx	X.XX
Difference in mean interaction with caregivers z-score in milk-free LNS compared to milk-containing LNS	XX.XX	xx.xx to xx.xx	X.XX

Table 2. Regression results of the difference between the milk-containing and milk-free LNS

	Control	10g milk	20g milk	20g milk-	40g milk	40g milk-	P-	7
age.								
Table 3 Results of the logistic regressio	n comparing	g the prevalenc	e of developme	ental delay in th	e intervention	n groups at 18 i	months c	of

Variable	Control	10g milk LNS	20g milk LNS	20g milk- free LNS	40g milk LNS	40g milk- free LNS	P- value
Proportion severe gross motor delay, No. /total	xxx/xxx	xxx/xxx	xxx/xxx	xxx/xxx	xxx/xxx	xxx/xxx	X.XX
No. (%)	$(xx.x\%)^x$	(xx.x%),	(xx.x%),	(xx.x%),	(xx.x%),	(xx.x%),	
Relative risk (95% CI)		x.xx (x.xx- x.xx) ^x					
Proportion moderate to severe gross motor	xxx/xxx	xxx/xxx	xxx/xxx	xxx/xxx	xxx/xxx	xxx/xxx	X.XX
delay, No. /total No. (%)	$(xx.x\%)^x$	(xx.x%),	(xx.x%),	(xx.x%),	(xx.x%),	(xx.x%),	
Relative risk (95% CI)		x.xx (x.xx- x.xx) ^x					
Proportion severe fine motor delay, No. /total	xxx/xxx	xxx/xxx	xxx/xxx	xxx/xxx	xxx/xxx	xxx/xxx	X.XX
No. (%)	$(xx.x\%)^x$	(xx.x%),	(xx.x%),	(xx.x%),	(xx.x%),	(xx.x%),	
Relative risk (95% CI)		x.xx (x.xx- x.xx) ^x					
Proportion moderate to severe fine motor delay,	xxx/xxx	xxx/xxx	xxx/xxx	xxx/xxx	xxx/xxx	xxx/xxx	X.XX
No. /total No. (%)	$(xx.x\%)^x$	(xx.x%),	(xx.x%),	(xx.x%),	(xx.x%),	(xx.x%),	
Relative risk (95% CI)		x.xx (x.xx- x.xx) ^x					
Proportion severe psychomotor delay, No. /total	xxx/xxx	xxx/xxx	xxx/xxx	xxx/xxx	xxx/xxx	xxx/xxx	X.XX
No. (%)	$(xx.x\%)^x$	(xx.x%),	(xx.x%),	(xx.x%),	(XX.X%),	(xx.x%),	
Relative risk (95% CI)		x.xx (x.xx- x.xx) ^x					

Proportion moderate to severe psychomotor	xxx/xxx	xxx/xxx	xxx/xxx	xxx/xxx	xxx/xxx	xxx/xxx	X.XX
delay, No. /total No. (%)	$(xx.x\%)^x$	(xx.x%),	(xx.x%),	(xx.x%),	(xx.x%),	(xx.x%),	
		x.xx (x.xx-	x.xx (x.xx-	x.xx (x.xx-	x.xx (x.xx-	x.xx (x.xx-	
Relative fisk (95% CI)		x.xx) ^x	x.xx) ^x	x.xx) ^x	x.xx) ^x	$(x.xx)^{x}$	
Description and the second states No. (444-1 No.							
Proportion severe language delay, No. /total No.		XXX/XXX	XXX/XXX	XXX/XXX	XXX/XXX	XXX/XXX	X.XX
(%)	$(XX.X\%)^{x}$	(XX.X%),	(XX.X%),	(XX.X%),	(XX.X%),	(XX.X%),	
Polativo rick (05% CI)		x.xx (x.xx-	x.xx (x.xx-	x.xx (x.xx-	x.xx (x.xx-	x.xx (x.xx-	
Kelative fisk (95% CI)		x.xx) ^x	$(x.xx)^{x}$	$(x.xx)^{x}$	$(x.xx)^{x}$	$(x.xx)^{x}$	
Proportion moderate to severe language delay	xxx/xxx	xxx/xxx	xxx/xxx	xxx/xxx	xxx/xxx	xxx/xxx	X.XX
No /total No (%)	$(\mathbf{x}\mathbf{x}\mathbf{x}\%)^{\mathrm{X}}$	$(\mathbf{x}\mathbf{x},\mathbf{x}\%)$	$(\mathbf{x}\mathbf{x},\mathbf{x}\%)$	$(\mathbf{x}\mathbf{x},\mathbf{x}\%)$	$(\mathbf{x}\mathbf{x},\mathbf{x}\%)$	$(\mathbf{x}\mathbf{x},\mathbf{x}\%)$	
	(ЛЛ.Л /0)	(XX,X/0),	(XX, X/0),	(XX, X/0),	(XX, X / 0),	$(\Lambda\Lambda\Lambda/0),$	
Relative risk (95% CI)		$X.XX (X.XX^{-})^{X}$	$X.XX (X.XX^{-})$	$X.XX (X.XX^{-})$	$X.XX (X.XX^{-})^{X}$	$X.XX (X.XX^{-})$	
		X.XX)	X.XX)	X.XX)	X.XX)	X.XX)	
Proportion severe socio-emotional delay, No.	xxx/xxx	xxx/xxx	xxx/xxx	xxx/xxx	xxx/xxx	xxx/xxx	X.XX
/total No. (%)	$(xx.x\%)^x$	(xx.x%),	(xx.x%),	(xx.x%),	(xx.x%),	(xx.x%),	
		x.xx (x.xx-	x.xx (x.xx-	x.xx (x.xx-	x.xx (x.xx-	x.xx (x.xx-	
Relative risk (95% CI)		x.xx) ^x	x.xx) ^x	$(x.xx)^{x}$	x.xx) ^x	$(x.xx)^{x}$	
Proportion moderate to severe socio-emotional	XXX/XXX	xxx/xxx	xxx/xxx	xxx/xxx	xxx/xxx	xxx/xxx	X.XX
delay, No. /total No. (%)	$(XX.X\%)^{x}$	(xx.x%),	(xx.x%),	(xx.x%),	(xx.x%),	(xx.x%),	
Polative risk (05% CI)		x.xx (x.xx-	x.xx (x.xx-	x.xx (x.xx-	x.xx (x.xx-	x.xx (x.xx-	
Kelative fisk (95% CI)		$(x.xx)^{x}$	$(x.xx)^{x}$	$(x.xx)^{x}$	$(x.xx)^{x}$	$(x.xx)^{x}$	
Proportion severe executive function delay. No	xxx/xxx	xxx/xxx	xxx/xxx	 	xxx/xxx	xxx/xxx	x xx
/total No. (%)	$()^X$	$(\mathbf{x}\mathbf{x},\mathbf{x}0')$	(xx x0/)	(xx x0/)	$(\mathbf{x}\mathbf{x},\mathbf{x}0/2)$	(xx x0/)	Λ.ΛΛ
			I I A A A 7/0 I	1 1 3 3 3 70 1	1 1 A A A 70 L	L L A A . A 70 L	1
	(XX.X%)	$(\Lambda\Lambda\Lambda\Lambda/0),$	(M.M. / 0),	(MM.M.70),	(IIIIII/0);	(/////////////////////////////////////	
Relative risk (95% CI)	(XX.X%)	(XX.X70), X.XX (X.XX-	X.XX (X.XX-	X.XX (X.XX-	X.XX (X.XX-	X.XX (X.XX-	
Relative risk (95% CI)	(XX.X%)	(XX.X70), X.XX (X.XX- X.XX) ^X	(AAAA/O), x.xx (x.xx- x.xx) ^x	$\begin{array}{c} (X,X,X,V),\\ X,XX,X,X,X,X,X,X,X,X,X,X,X,X,X,X,X,X,$	x.xx (x.xx- x.xx) ^x	(

Proportion moderate to severe executive	xxx/xxx	xxx/xxx	xxx/xxx	xxx/xxx	xxx/xxx	xxx/xxx	X.XX
function delay, No. /total No. (%)	$(xx.x\%)^x$	(xx.x%),	(xx.x%),	(xx.x%),	(xx.x%),	(xx.x%),	
Relative risk (95% CI)		x.xx (x.xx- x.xx) ^x					

Prevention of Linear Growth Faltering in Infants and Young Children With Lipid-based Nutrient Supplements (iLiNS-DOSE)

Statistical Analysis Plan

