12.6 Covariate adjustment

The final decision on the use of covariates in main analyses will be decided based on preliminary analyses on the final dataset that includes information on the clustering of participants in the same group but does not provide information on the actual intervention delivered to each group.

At this stage, four different regression models for change in LAZ will be constructed, first of these with no covariate adjustments and models 2-4 with various adjustments. If the pointestimates for the regression co-efficient for the intervention group differ in any of the models by more than 10% from that in the unadjusted analyses, the adjusted analysis will be primarily presented in the eventual publications. If all the differences are smaller than 10% (Maldonado & Greenland, 1993), the results in the tables will be shown without covariate adjustments, but model 4 results will be provided in the text as supplementary information.

The four models include:

- 1. No covariate adjustment
- 2. Adjustment for baseline LAZ-score
- 3. Adjustment for baseline WHZ-score
- 4. Adjustment for baseline LAZ-score and baseline WHZ-score and for any of the variables presented in tables 1a and 1b showing statistically significant association (at p<0.1 level) with the change in LAZ-score

13 Storage and release of data

The data meta-data will be stored in a tailor-made hierarchical database, consisting of a MS Access front-end and MySQL tables in the back-end. The database, associated metadata, and form –specific do-files that contain all cumulative data corrections for the respective data collection forms are stored at a computer server at the University of Tampere and daily copied to

a server at the Mangochi research site, University of Malawi. A study statistician ([name]) acts as the manager for these data.

When an investigator wishes to perform certain analyses, s/he will request the respective data from the above-indicated data manager. The data manager will export all the data from the respective data collection form into an excel or Stata file, run the cumulative data correction do-file and then provide the corrected data, together with the syntax for the correction do file (that documents all the completed data editions) to the person requesting the data.

The databases and the do-files will be named with systematic naming format and stored at the central server at the University of Tampere. For each article, the following files will be stored:

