	6.1 Software
	6.2 Calculating z-scores
	6.3 Multiple comparisons
	6.4 Confidence intervals
	6.5 Interaction and effect modification
	6.6 Covariate adjustment
7.	References
8.	Tables
	Table 1 Comparison of developmental scores in the intervention groups at 18 months
	Table 2 Prevalence of developmental delay at 18 months of age 11

1. Study objectives

The main aim of the trial was to assess the safety and impact of supplementation with Lipidbased Nutrient Supplements (LNS) on linear growth of infants and young children and to identify individual, household, and village-level characteristics that modify the effects of LNS on child growth. A secondary aim is to similarly study the impact of LNS on various other (secondary) outcomes in the same target group.

The aim of the secondary analyses described in this appendix is to compare infants in 6 different intervention groups: dietary supplementation from age 6 to 18 months with 10 g, 20 g or 40 g per day milk-containing LNS, or 20 g or 40 g per day milk-free LNS, or nothing (delayed intervention) on the following outcomes:

- 1. 18-month motor development, language development, socio-emotional development, executive function, and interaction with caregivers
- 2. Prevalence of severe and moderate to severe delay in motor development, language development, socio-emotional development, and executive function

2. Hypotheses to be tested

- 1. 18-month scores in gross and fine motor development, language development, socioemotional development, executive function, and interaction with caregivers of infants provided with 10, 20, or 40 g/day of LNS from 6 to 18 months of age will be greater than that of infants who receive no dietary intervention at the same age.
- 2. 18-month scores in gross and fine motor development, language development, socioemotional development, executive function, and interaction with caregivers of infants receiving 20 or 40 g/day of LNS without milk from 6 to 18 months of age will not be lower than that of infants receiving a comparable intervention with milk-containing LNS.
- 3. 18-month scores in gross and fine motor development, language development, socioemotional development, executive function, and interaction with caregivers of infants provided with 20 or 40 g/day of LNS from 6 to 18 months of age will be greater than that of infants who receive 10g/day and that of infants provided with 40 g/day will be greater than that of infant who receive 20 g/day.

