Interaction with caregivers is calculated as the sum of the activities with adults in the past three days (*Form 25d Q 4.1.1* through Q 4.5.3).

4. Basis for the analysis: Intention to treat and per protocol

The basis for the analysis will be the same as that for the primary outcomes.

5. Presentation of the study findings and hypothesis testing

5.1 Comparison of the developmental scores at 18 months of age between intervention groups versus the control group

The group means and standard deviations for the gross motor score, fine motor score, psychomotor score, vocabulary score, socio-emotional score, and A not B task total number correct, total errors after set 1, and total trials completed, and the interaction with caregivers score will be presented as indicated in Table 1. Both raw scores and z-scores will be presented. The results of pairwise comparisons will be indicated by superscripts. Means that are significantly different from each other will be marked by different letters (e.g., a and b). Means that are not significantly different from each other will be marked by the same letter.

We will use a one-factor analysis of variance (ANOVA) (or ANCOVA in analyses that include covariates, as specified in section 6.6) to test for differences between the six groups. If the group effect is significant at the level of p < .07, we will use Tukey-Kramer's test for post-hoc pairwise comparisons between each intervention group and the control group. The null-hypothesis of LNS having no impact on development will be rejected for each comparison that yields a Tukey-Kramer's adjusted p-value < 0.05.

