Appendix 04: The effect of LNS on physical activity (added on 24.05.2013)

Table of Contents

1	Stu	dy objectives
2	Hy	potheses to be tested
3	De	finition of the physical activity outcomes
4	Ba	sis for the analysis: Intention to treat and per protocol
5	Tir	ne points for the analyses
6	Pre	sentation of the study findings and hypothesis testing
	6.1	Success of enrolment, follow-up and physical activity measurement
	6.2	Baseline information
	6.3 group	Comparison of physical activity between intervention groups versus the control 4
7	Ge	neral notes on statistical methods
	7.1	Software
	7.2	Preparing physical activity data for analysis
	7.3	Preparing anthropometric data for analysis
	7.4	Multiple comparisons
	7.5	Confidence intervals
	7.6	Interaction and effect modification
	7.7	Covariate adjustment
8	Re	ferences
9	Leg	gends to the figures
10	Fig	ures
	Figur	e 1. Participant flow
	Figur	e 2. Box-Whisker plots of time in moderate-to-vigorous physical activity by groups 8
Та	bles.	
Тε	ble 1	Baseline characteristics of participants at baseline and 18 months
	Table	2 Physical activity at the trial groups

1 Study objectives

The main aim of sub-study is to assess impact of LNS supplementation on physical activity of children at the age of 18 months. This will be done by comparing physical activity of children in the six intervention groups: dietary supplementation with 10 g, 20 g or 40 g/day milk-containing LNS, 20 g or 40 g/day milk-free LNS or nothing (delayed intervention).

A secondary aim is to assess dose response between LNS supplementation and physical activity. In addition, we will explore possible effect modifiers of the impact of LNS supplementation on physical activity.

2 Hypotheses to be tested

The mean physical activity of infants provided with 10, 20, or 40 g/day of LNS from 6 to 18 months of age is greater than that of infants who receive no dietary intervention at the same age.

3 Definition of the physical activity outcomes

Primary outcome: mean accelerometer counts

Physical activity counts used in the analysis are vector magnitude counts, calculated by taking the square root of the sum of squared activity counts of each three axis. The mean counts/15 s of each day will be averaged over all valid days to produce mean of means for each participant.

Data for physical activity will be considered missing if the actual measurement date was over 30 days from the target date.

Secondary outcomes

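### Appendix 2 lets the KDI models adjust for the child's behaviour at the 18-month test on the strength of an undefined 'not different' screen, and that adjusted result can become the one primarily presented

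*SAP*

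**What the plan says.** Appendix 2 section 6.6 fits three models: unadjusted; adjusted for age at assessment; and adjusted for age, baseline LAZ and WHZ, and any variable from main Tables 1a and 1b associated with the score at p<0.1. It then lists further candidates. For the KDI scores these are "the child's mood, interaction with the tester, and activity level during testing, if they are not different between supplement groups", taken from Form 25a Q 3.1 to 3.3. Section 3 takes the gross motor items from the same form. A second candidate is "Family care indicators score, if this score is not different between supplement groups".

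Three other places matter:

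- On choosing between models, section 6.6 says: "The same procedure will be followed as for the main analyses, with three models rather than four models". In the main SAP, section 12.6, if an adjusted estimate moves "by more than 10% from that in the unadjusted analyses, the adjusted analysis will be primarily presented in the eventual publications".
- Appendix 2 section 5.1 uses ANOVA, "or ANCOVA in analyses that include covariates, as specified in section 6.6) to test for differences between the six groups". The title of Table 1 in Appendix 2 refers to ANCOVA, and its footnotes will name the covariates used for each outcome.
- Appendix 4 section 2 hypothesises: "The mean physical activity of infants provided with 10, 20, or 40 g/day of LNS from 6 to 18 months of age is greater" than in unsupplemented infants.

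**The concern.** Mood, engagement with the tester and activity during the session are seen once, when the child is about 18 months old and has been supplemented for up to a year. If LNS makes a child livelier or more engaged, and such children score higher on motor items, these variables lie on the path from supplement to score. Adjusting for them removes that part of the effect and leaves only the remainder.

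The 'not different' condition is evidently meant to prevent this, but it cannot. It names no test, significance level or equivalence margin. If read as a significance test, it admits any affected variable whose shift is too small to detect reliably. The 10% rule adds to the problem: a covariate that carries part of the effect is one that will move the estimate, so the rule tends to promote the model that contains it. What is at stake is the KDI comparison of LNS with control, where a true benefit could be under-reported.

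**Working it through.** The plan gives no figure here, so there is none to reproduce. The check asks how often the screen would admit a variable that LNS has really changed, and what adjustment would then do.

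**Inputs.** From the SAP: 1932 randomised to six groups (section 2), so 1932/6 = 322 per arm if allocation was equal. The number tested at 18 months is not stated, so 250 per arm is also shown as an assumption. Also assumed: the screen is a six-group one-way ANOVA, and the covariate (SD 1) is raised by d in all five LNS arms and not in control.

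**Step 1: admission rate.** With one group mean at 0 and five at d, the sum of squared deviations from the grand mean is (5/6)d², so the non-centrality is λ = n × (5/6) × d². For n = 250 and d = 0.15, λ = 250 × 0.8333 × 0.0225 = 4.69. The admission rate is the probability that a non-central F with 5 and 6n − 6 df falls below the critical value (2.22 at alpha 0.05).

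| n per arm | d (SD) | λ | alpha 0.05 | alpha 0.07 | alpha 0.10 |
|---|---|---|---|---|---|
| 250 | 0.10 | 2.08 | 84% | 80% | 74% |
| 250 | 0.15 | 4.69 | 66% | 60% | 54% |
| 250 | 0.20 | 8.33 | 42% | 36% | 30% |
| 322 | 0.10 | 2.68 | 80% | 75% | 69% |
| 322 | 0.15 | 6.04 | 57% | 51% | 44% |
| 322 | 0.20 | 10.73 | 29% | 24% | 19% |

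The 0.07 column is included because Appendix 2 section 5.1 uses that level as its gate for the outcome comparisons.

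**Step 2: what adjustment removes.** If the covariate is a mediator with within-group correlation r to the score, the adjusted estimate targets the total effect minus about d × r. With r assumed to be 0.4 to 0.5, this is 0.15 × 0.4 = 0.06 SD at the low end and 0.20 × 0.5 = 0.10 SD at the high end.

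**Step 3: what happens after the screen.** A simulation (4,000 runs per setting; n = 250 or 322, d = 0.10 to 0.20, slope 0.3 or 0.5, true total effect 0.15 SD, screen alpha 0.05) compared the pooled LNS arms with control in trials that passed the screen. The unadjusted estimate averaged 0.12 to 0.15 SD and the adjusted estimate 0.05 to 0.12 SD. The two differed by more than 10% in 77% to 99% of those trials. That last range includes chance imbalance as well as mediation, so it shows how readily the rule is triggered, not how large the bias is.

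**The case against.** The strongest defence is that the authors saw the risk and wrote a condition to guard against it. The text says only that the variables will be considered, an unadjusted model is always fitted, and footnotes disclose the covariates. In-session mood and engagement may also be mostly measurement noise, and adjusting for noise unrelated to treatment only sharpens the estimate. All of this is fair, and it makes the harm conditional. It does not repair the rule, because the screen cannot tell a noise variable from a modestly affected one.

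It is also fair that the observed covariate difference is smaller in trials that pass the screen. At 250 per arm it averages 0.118 SD (d = 0.15) or 0.142 SD (d = 0.20). The adjusted and unadjusted results would then differ by roughly 0.118 × 0.4 = 0.05 to 0.142 × 0.5 = 0.07 SD, less than the 0.06 to 0.10 above. The adjusted estimate still targets the direct effect only, so the shortfall from the total effect remains.

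A reader might infer more than the SAP supports in four respects:

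- **Milk-free v milk.** The attenuation should not be set against the 0.2 non-inferiority margin in Appendix 2 section 5.2. That margin governs milk-free v milk-containing LNS. If all LNS arms shift equally, the expected covariate difference between those arms is zero. The contrast is affected only if milk content itself changes test behaviour, which the SAP does not hypothesise.
- **Family care.** The SAP does not say when this score was measured. Section 6.5 lists it as an effect modifier alongside enrolment characteristics. The condition "if this score is not different between supplement groups" would be unnecessary for a baseline variable, but that is only a hint. The objection applies only if the score was taken after enrolment.
- **Appendix 4.** It concerns accelerometer counts over several days of wear, which are related to activity in a test session but not the same. It makes an effect plausible; it does not state one.
- **Scope.** The behaviour items are offered for the KDI scores only, not for the other developmental outcomes.

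**Conclusion.** The point holds for the three test-session items in the KDI models. They are post-randomisation variables that LNS could change, the screen that admits them is undefined, and the 10% rule can make the resulting model the primarily presented one. With a 0.05 screen and shifts of 0.10 to 0.20 SD, an affected variable is admitted in 42% to 84% of trials at 250 per arm and 29% to 80% at 322. If the variable mediates the effect and both links share its sign, the LNS v control difference loses about 0.06 to 0.10 SD at the assumed d of 0.15 to 0.20 and r of 0.4 to 0.5. Arm size at testing, screen level, shift and correlation are all assumptions. Without mediation in that direction, this attenuation does not arise. These are secondary outcomes and the bias is conditional, so the change is one that should be made; it does not put the trial's primary conclusion in doubt.

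**What to change.** In Appendix 2 section 6.6, limit covariates in the treatment-effect models to variables fixed at or before enrolment, plus age at assessment and, for the language scores, the language variables already listed. Remove the 'not different between groups' condition as a route into these models. Report adjustment for mood, interaction with the tester and activity during testing only in a labelled sensitivity analysis that the 10% rule cannot promote. State when the family care score was measured. Keep it in the main models only if that was at or before enrolment; otherwise move it to the sensitivity analysis as well.

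The cost is a change of wording and some precision. The loss is slight unless test behaviour is strongly related to the score. At the assumed r of 0.4 to 0.5, standard errors would be at most about 9% to 15% larger than with adjustment (1/√(1 − 0.16) = 1.09; 1/√(1 − 0.25) = 1.15), and less where other covariates explain the same variation.
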